4.4 Patients or Partners of Patients of Reproductive Potential

Pregnancy is an exclusion criterion for patients enrolled to receive study treatment. WOCBP or male patients of reproductive potential with female partners of childbearing potential must not be considering getting pregnant and must avoid pregnancy during the study and for at least 6 months (female patients) or 3 months (partners of male patients of reproductive potential) after the last dose of rucaparib or longer if requested by local authorities.

Female patients of childbearing potential must have a negative pregnancy test result ≤ 3 days prior to administration of the first dose of rucaparib in this study. In addition, a pregnancy test must be performed ≤ 3 days prior to Day 1 of every cycle during the Treatment Phase and at the time of treatment discontinuation. Pregnancy testing will be conducted locally. Treatment should be discontinued immediately in any woman found to have a positive pregnancy test while taking rucaparib.

Male patients are required to use a condom during sex with a partner to avoid the possibility of exposure of the partner to rucaparib, regardless of whether the partner is a WOCBP or not, or who are pregnant. Male patients must not make semen donations during treatment and for 3 months following the last dose of rucaparib.

Male patients are considered to be of reproductive potential unless permanently sterile by bilateral orchiectomy or vasectomized with appropriate post-vasectomy documentation of absence of sperm in ejaculate.

Female patients or partners of male patients are considered to be of childbearing potential unless one of the following applies:

- Considered to be permanently sterile. Permanent sterilization includes hysterectomy, bilateral salpingectomy, and/or bilateral oophorectomy; or
- Is postmenopausal, defined as no menses for at least 12 months without an alternative medical cause. A high follicle-stimulating hormone (FSH) level consistently in the postmenopausal range (30 mIU/mL or higher) may be used to confirm a postmenopausal state in women not using hormonal contraception or hormonal replacement therapy; however, in the absence of 12 months of amenorrhea, a single FSH measurement is insufficient to confirm a postmenopausal state.

Female patients of reproductive potential must practice highly effective methods (failure rate < 1% per year) of contraception with their partners, if of reproductive potential, during treatment and for 6 months following the last dose of rucaparib or longer if requested by local authorities.

Male patients must practice highly effective methods (failure rate < 1% per year) of contraception with their female partners, if of reproductive potential, during treatment and for 3 months following the last dose of rucaparib or longer if requested by local authorities.

Highly effective contraception includes:

- Ongoing use of progesterone only injectable or implantable contraceptives;
- Placement of an intrauterine device (IUD) or intrauterine system (IUS);
- Bilateral tubal occlusion;
- Sexual abstinence as defined as complete or true abstinence, acceptable only when it is the usual and preferred lifestyle of the patient; periodic abstinence (eg, calendar, symptothermal, post-ovulation methods) is not acceptable; or
- Male sterilization, with appropriate post-vasectomy documentation of absence of sperm in ejaculate.

Female patients will be instructed to notify the investigator if pregnancy is discovered either during or within 6 months of completing treatment with rucaparib, and male patients will be instructed to notify the investigator if pregnancy is discovered in their female partner either during or within 3 months of completing treatment with rucaparib (refer to Section 8.5).

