Table 7-1 Schedule of Assessments

- ^d Patients rolling over to continued treatment with rucaparib in this study will sign consent prior to the End-of-Treatment (EOT) Visit of the parent study. Patients rolling over from LTFU in the parent study will sign consent prior to the first LTFU visit in the rollover study.
- ^e Adverse events (AEs) will be monitored but only serious AEs (SAEs)/adverse events of special interest (AESIs) are collected per Clovis Pharmacovigilance (PV) guidelines and reported in the Clovis PV database through 28 days after last dose of rucaparib (Post-treatment Follow-up Visit). Ongoing SAEs and AESIs at the time of the Post-treatment Follow-up Visit will be followed to resolution, stabilization, or lost to follow-up. After this visit, only SAEs considered as potentially related to study drug (including serious reports of pneumonitis or associated events, if considered to be related to study drug), and AESIs of MDS and AML irrespective of causality, will be reported. If a patient discontinues from treatment in the rollover study and begins a subsequent anticancer therapy, the sponsor will terminate collection of SAEs.
- ^f Women of childbearing potential (WOCBP) must have a negative pregnancy test result ≤ 3 days prior to the first dose of rucaparib in this study. A pregnancy test must be performed ≤3 days prior to Day 1 of every cycle from Cycle 2 and beyond during the treatment phase. Testing may be performed per institutional standard of care during treatment, and results must be reviewed prior to commencing a new cycle of rucaparib. A pregnancy test must be performed at the EOT Visit of the parent study and the Post-treatment Follow-up Visit of the rollover study. See Section 8.5 for reporting a positive pregnancy result.
- ^g More than 1 cycle of rucaparib can be dispensed, if deemed appropriate by investigator. Patients will be instructed to bring their rucaparib tablets and all containers (empty, partially used, and/or unopened) to each scheduled visit for reconciliation by site personnel.

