8.5 Pregnancy or Drug Exposure During Pregnancy

If a patient becomes pregnant during the study the investigator is to stop dosing with investigational product(s) immediately.

A pregnancy is not considered to be an AE or SAE; however, any pregnancy occurring in a study patient or partner of a study patient during study participation or within 6 months of the last dose for female patients, and within 3 months of last dose for partners of male study patients, must be reported to the sponsor using the Pregnancy Report Form within the same timelines as an SAE.

All pregnancies will be followed through to outcome, if possible. Once the outcome of the pregnancy is known, the Pregnancy Outcome Report Form is to be completed and reported to the sponsor.

AEs, SAEs, or AESIs that occur during pregnancy will be assessed and processed according to the AE or SAE/AESI processes using the appropriate SAE/AESI forms.

If any female partner becomes pregnant by a male study patient while he is receiving rucaparib, or within 3 months after the last dose of rucaparib, she will be asked to provide optional consent to allow follow-up until final outcome/delivery to determine if rucaparib has any effect on the pregnancy and fetal development.

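### Section 4.4 ties the patient's pregnancy notification to discovery and Section 8.5 ties reporting to occurrence, so a pregnancy that begins late in the window may be missed

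*Protocol*

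**What the plan says.** The last paragraph of Section 4.4 sets out what patients will be told. A female patient is to notify the investigator "if pregnancy is discovered either during or within 6 months of completing treatment with rucaparib". A male patient is to do so "if pregnancy is discovered in their female partner either during or within 3 months of completing treatment with rucaparib". The paragraph then refers the reader to Section 8.5.

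Section 8.5 sets the duty to report to the sponsor, on the same timelines as an SAE. Where the patient is a woman, it covers "any pregnancy occurring in a study patient or partner of a study patient during study participation or within 6 months of the last dose". The limit where the patient is a man is "within 3 months of last dose for partners of male study patients, must be reported to the sponsor using the Pregnancy Report Form". Its paragraph on following up a partner's pregnancy also goes by the start of the pregnancy: "If any female partner becomes pregnant by a male study patient while he is receiving rucaparib, or within 3 months after the last dose".

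On testing, footnote f to Table 7-1 (Section 7.1) says: "A pregnancy test must be performed at the EOT Visit of the parent study and the Post-treatment Follow-up Visit of the rollover study". The table restricts the test to women of childbearing potential among the patients and marks none in the long-term follow-up (LTFU) column. Under Study Duration, the synopsis keeps treated patients enrolled through 28 days after their last dose. LTFU beyond that needs consent and applies only where the parent study's objectives call for it (Section 3.2.3).

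**The concern.** The two sections use the same window lengths but different events to decide whether a pregnancy falls inside them. Recognition comes after conception, so the mismatch works in one direction: the instruction to patients covers fewer pregnancies than the site's reporting duty.

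The site can report only what it learns. Between the visit at about day 28 and the end of month 3 or 6, it will learn of a pregnancy mainly because the patient says so. The narrower wording therefore sits at the step on which reporting depends. At stake is complete capture of pregnancies exposed within the protocol's own risk window, which Section 8.5 wants followed to outcome where possible.

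**Working it through.** The plan gives no figure on this point to reproduce. The check is a comparison of texts, followed by a rough bound on size.

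**Step 1: the triggers side by side**

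| | Section 4.4 (patient's instruction) | Section 8.5 (report to sponsor) |
|---|---|---|
| Event that counts | pregnancy is discovered | pregnancy occurs or begins |
| Female patients | 6 months | 6 months |
| Partners of male patients | 3 months | 3 months |
| Counted from | completing treatment | last dose |

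I take completing treatment and last dose as the same date, since the protocol shows no difference between them.

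**Step 2: which pregnancies fall between**

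Let W be the window, c the time of conception after the last dose, and L the lag to recognition.

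- Section 8.5 applies if c ≤ W.
- The Section 4.4 instruction applies if c + L ≤ W.
- The gap is W − L < c ≤ W, a tail of length L at the end of the window.

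Examples with an assumed L of 6 weeks:

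- Female patient, W about 26 weeks, c = 24: 24 ≤ 26, so reportable; 24 + 6 = 30 > 26, so outside the instruction.
- Partner, W about 13 weeks, c = 11: 11 ≤ 13, so reportable; 11 + 6 = 17 > 13, so outside the instruction.

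**Step 3: does a scheduled step close the gap?**

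- The last protocol test is about 4 weeks after the last dose. For female patients, about 26 − 4 = 22 weeks of the window follow it with no test.
- Partners are not tested at any point.
- LTFU contact, where it applies, is about every 12 weeks, but Table 7-1 lists no pregnancy enquiry there. Section 8.5 states that a pregnancy is not itself an AE or SAE, so adverse event monitoring need not bring it out.

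Nothing scheduled clearly closes the gap.

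**Step 4: size**

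Section 4.4 requires contraception with a failure rate under 1% per year throughout both windows. The lag is not in the documents; I assume 2 to 8 weeks. With adherence and a constant rate, the chance of a conception in the tail, per woman at risk, is below 1% × L/52:

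- L = 2 weeks: 1% × 2/52 = 0.04%
- L = 4 weeks: 1% × 4/52 = 0.08%
- L = 8 weeks: 1% × 8/52 = 0.15%

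That is fewer than about 0.4 to 1.5 per 1,000 women at risk. Poor adherence would raise it. Section 4.1 leaves the number of patients open, so no expected count can be given.

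**The case against.** The strongest reply is that Section 4.4 does not limit the duty. It gives an affirmative instruction, does not say that later discoveries need not be mentioned, and points to Section 8.5, which binds the investigator whenever the site learns of a pregnancy. This stands against any claim that such pregnancies are certain to go unreported. It does not remove the mismatch: the cross-reference speaks to readers of the protocol, while the sentence fixes what patients are told.

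There are also other routes. A congenital anomaly is an SAE under Section 8.2, and potentially related SAEs stay reportable after the 28-day visit, unless subsequent anticancer therapy has ended SAE collection. Patients in LTFU are contacted regularly. This stands in part. The SAE route would find only pregnancies with a bad outcome, and LTFU does not cover every patient.

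Finally, no objective in Section 2 concerns pregnancy and Section 9.4 plans no safety analysis. That stands in full and limits the weight of the point.

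**Conclusion.** The mismatch is real. A pregnancy that begins inside the window and is recognised after it is reportable under Section 8.5 but falls outside the Section 4.4 instruction, and it may be missed. The expected number is very small, below about 0.4 to 1.5 per 1,000 women at risk if contraception is used as required and recognition takes 2 to 8 weeks. No sample size, error rate or planned analysis changes. It is still worth correcting, because the reporting duty is mandatory and the change is small.

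The documents do not support four stronger readings that a reader might infer:

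- **That late conceptions are never notified.** A patient may still tell the site, which must then report. The text supports only that they may be missed.
- **That the loss is greatest for partners of male patients.** As a share of the window it looks so: at a 4-week lag, 4/13 = 31% against 4/26 = 15%. The uncovered tail is 4 weeks in both groups, so at equal conception rates the loss per woman is the same. Only the denominator differs.
- **That longer pregnancy avoidance at the request of local authorities leaves a further gap.** The protocol states no such longer period, the two sections agree at 6 and 3 months, and the consent text is not at hand.
- **That completing treatment and last dose are different anchors.** No differing date is shown.

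**What to change.** Reconcile the two sections by rewording the last paragraph of Section 4.4. Patients should be told to notify the investigator of any pregnancy, their own or a partner's, that begins within the window defined in Section 8.5, whenever it is discovered. Change the matching consent text in the same way. Section 8.5 and the window lengths can stay as they are.

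The cost is one sentence in the protocol and a consent update that needs IRB/IEC approval (Section 10.7), with re-consent of current patients if the IRB/IEC mandates it (Section 10.2.2). A few more pregnancy reports may follow. No visit or test is added.

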4.5 Compliance With Inclusion/Exclusion Criteria

All inclusion/exclusion criteria must be met for the prospective participant to enroll. Neither the investigator, nor the sponsor/designee, may allow a prospective participant who has not met the inclusion/exclusion criteria to enter the study.

5 STUDY TREATMENT

5.1 Description of Investigational Product and Storage

5.1.1 Rucaparib

A brief description of the investigational product is provided in Table 5-1.

Drug Name:	Rucaparib
INN:	Rucaparib
Formulation:	Tablet; film coated; 200 mg (blue, round, debossed with C2), 250 mg (white, diamond shape, debossed with C25), 300 mg (yellow, oval, debossed with C3).
How Supplied:	200 mg, 250 mg, and 300 mg (as free base) strength tablets in 60 count bottles. Patients may receive one or more strengths.
Storage Conditions:	15–30°C (59–86°F).

 Table 5-1
 Description of Study Treatment

Abbreviation: INN = International Nonproprietary Name.

5.2 Packaging and Labeling

5.2.1 Rucaparib

Rucaparib tablets are provided in 60-count high-density polyethylene (HDPE) bottles with child resistant caps and should be stored in the provided containers between 15°C and 30°C (59°F and 86°F). Patients will be dispensed one or more strengths depending on their dose of rucaparib. The number of bottles of each strength dispensed will be sufficient to supply at least one 28-day treatment cycle, including a small overage (see Section 5.4.1).

Study drug containers containing rucaparib tablets will be labeled according to national regulations for investigational products and inventory will be managed by the use of Interactive Response Technology (IRT).

5.3 Measures to Minimize Bias: Randomization and Blinding

This is an open-label study; the investigational product will not be blinded.

5.4 **Preparation and Administration of Protocol-specified Treatment**

5.4.1 Rucaparib

The investigator or designee will be responsible for distributing rucaparib tablets to all patients.

The dose of rucaparib is that which was last received in the parent study, or as deemed appropriate by the investigator and based on available dose strength tablets. Patients may take rucaparib with or without food. Each dose should be taken with water. Tablets should be swallowed whole without crushing or chewing. Tablet strength combinations shall be determined by the IRT.

Patients should take rucaparib doses as close to 12 hours apart as possible, preferably at the same times every day. If a patient misses a dose (ie, does not take it within 4 hours of the scheduled time), he/she should skip the missed dose and resume taking rucaparib with the next scheduled dose. Missed or vomited doses should not be made up.

More than 1 cycle of rucaparib can be dispensed, if deemed appropriate by the investigator (see Section 7.1). Patients will be instructed to bring their rucaparib tablets and all containers (empty, partially used, and/or unopened) to the next scheduled visit for reconciliation by site personnel.

5.5 Dose Modifications of Protocol-specified Treatment

Doses of rucaparib may be interrupted or delayed for toxicity and other protocol-specified criteria. Dose reductions are permitted for rucaparib. Treatment may be discontinued due to withdrawal of consent, unacceptable toxicity, disease progression, or termination of the study, whichever occurs first.

The date of last dose and reason for discontinuation should be captured on the appropriate eCRF; dose modifications (ie, interruption, reduction, and/or re-escalation) are not required to be recorded.

Refer to the current IB or regional prescribing information for comprehensive information on rucaparib.

Dose interruption and re-treatment of rucaparib are to be based on the criteria presented in Table 5-2.

Advance Event including	Severity	Rucaparib		
Laboratory Abnormalities	(CTCAE Grade)	Treatment Interruption	Re-treatment	
ALT/AST elevation (in the absence of other signs of liver dysfunction)	3	Continuation of dosing permitted provided total bilirubin is < ULN and ALP is < 3 x ULN; monitor LFTs weekly; Hold if levels do not decline within 2 weeks or if levels increase	≤ NCI-CTCAE Grade 2	
ALT/AST elevation	LT/AST elevation 4 Hold		≤ NCI-CTCAE Grade 2	
ALT or AST elevations (> 3 × ULN) AND Total bilirubin (> 2 × ULN) - Suspected DILI [Section 8.8]	NA	Hold ^a ; Monitor LFTs weekly If DILI is confirmed, treatment should be permanently discontinued	≤ NCI-CTCAE Grade 1 (or baseline)	

Table 5-2 Dose Interruption and Re-Treatment Criteria for Rucaparib

Abbreviations: ALP = alkaline phosphatase; ALT = alanine aminotransferase; AST = aspartate aminotransferase; DILI = drug-induced liver injury; INR = international normalized ratio; LFT = liver functions test; NCI-CTCAE = National Cancer Institute Common Terminology Criteria for Adverse Events; ULN = upper limit of normal.

^a Evaluate patient for the presence of confounding factors, including malignant disease in the liver, co-administration of other suspect drugs, cholestasis, and viral or autoimmune hepatitis, that could have caused the laboratory abnormalities. Other laboratory investigations of liver function such as INR should be implemented as indicated. If no alternative cause is identified, rucaparib must be permanently discontinued. Patients should be followed until all abnormalities have returned to normal, returned to baseline levels, or an alternative cause is found to explain the combination of the increased transaminases and total bilirubin.

5.5.1 Rucaparib Dose Modification Criteria

The rucaparib dose may be reduced as needed, per investigator decision. Refer to Section 5.1.1 for available dose strengths.

Dose escalation upon resolution of toxicity to \leq National Cancer Institute Common Terminology Criteria for Adverse Events (NCI-CTCAE)¹ Grade 1 is permitted at the discretion of the investigator.

5.5.1.1 Management of anemia

If anemia CTCAE Grade \geq 3 occurs and persists for > 14 days, or a dependence upon blood transfusions occurs, then weekly complete blood counts are recommended until resolution of the anemia to \leq Grade 1. If after 42 days of treatment interruption anemia has not improved to Grade \leq 1, a referral to a hematologist and analysis of the bone marrow according to institutional standard practice is recommended.

Refer to Sections 8.3 and 8.6 of the protocol for additional information regarding classification and reporting of MDS or AML as an AESI.

5.5.1.2 Management of new or worsening pulmonary symptoms

If new or worsening unexplained pulmonary symptoms suggestive of pneumonitis (including, but not limited to, dyspnea) occur, or a deterioration of pulmonary function is observed, and/or radiologic abnormality is detected in the lungs, and this occurs in the absence of any clear diagnosis, a diagnostic workup (including high resolution computed tomography [CT] scan) in consultation with a pulmonologist should be performed in order to rule out pneumonitis. During this time, treatment with rucaparib may be interrupted or continued per investigator discretion.

Following investigation, if pneumonitis is not confirmed, treatment with rucaparib may be resumed/continued as deemed appropriate by the investigator and in accordance with the study protocol directions for management of AEs. All confirmed events of pneumonitis should be treated as appropriate per medical judgement and institutional guidelines. If the event resolves and retreatment with rucaparib is being considered, please consult the study Medical Monitor. Retreatment with rucaparib may be resumed at the current or a reduced dose, if appropriate.

Refer to Sections 8.3 and 8.6 of the protocol for additional information regarding classification and reporting of pneumonitis (and related events) as an AESI.

5.5.2 Rucaparib Discontinuation

Treatment should be continued until it is determined by the investigator that no further clinical benefit can be achieved.

Rucaparib should be permanently discontinued for any of the following:

- Confirmed diagnosis of MDS or AML;
- Pregnancy (see Section 8.5)

5.6 Treatment Compliance

Dosing diaries will not be used in this study. Study site personnel should review dosing information with the patient (or legally authorized representative, where acceptable according to national law and/or local regulations) on scheduled clinic visit days, providing instructions regarding dose, dose frequency and the number of tablets to be taken for each dose. Patients (or legally authorized representative, where acceptable according to national law and/or local regulations) will be instructed to keep all unused tablets and containers (empty, partially used, and/or unopened) for accountability at scheduled clinic visits.

Every effort should be made to ensure patients return rucaparib containers/unused rucaparib at the end of each cycle of treatment. Study site personnel should conduct a verbal review of dosing with the patient and document the discussion in the patient's medical record.

